6. OBJECTIVES AND ENDPOINTS

Table 9: Study Objectives and Endpoints

OBJECTIVES	ENDPOINTS
Primary	
Evaluate the safety of UX053 in adults with GSD III	The incidence and severity of TEAEs, serious TEAEs, and related TEAEs in the SAD and RD cohorts
Secondary	
Characterize the PK of UX053 in adults with GSD III	PK parameters of AGL mRNA and ATX95, which may include T_{max} , C_{max} , AUC_{last} , AUC_{inf} , AUC_{tau} (RD cohorts only), R_{AUC} (RD cohorts only), T_{last} , $T_{1/2}$, CL, V_{ss}

AGL, amylo- α -1,6-glucosidase 4-alpha-glucanotransferase; AUC, area under the concentration-time curve; AUC_{inf} , AUC from time 0 to infinity; AUC_{last} , AUC from time 0 to the last measurable concentration; AUC_{tau} , AUC from time 0 to end of dosing period; CL, clearance; C_{max} , maximum observed concentration; PK, pharmacokinetics; R_{AUC} , accumulation ratio (calculated as AUC after repeat dose / AUC after a single dose); RD, Repeat Dose; SAD, Single Ascending Dose; $T_{1/2}$, half life; TEAE, treatment-emergent adverse events; T_{last} , time of last measurable concentration; T_{max} , time of maximum observed concentration; V_{ss} , volume of distribution at a steady state.

Tertiary CCI

and exploratory objectives CCI

and their corresponding endpoints are provided in the Statistical Analysis Plan (SAP).

7. INVESTIGATIONAL PLAN

7.1. Study Design

UX053-CL101 is a phase 1/2 FIH study to evaluate the safety, tolerability, and PK of SAD and RD of UX053 in patients with GSD III ([Figure 1](#)). The SAD cohorts will be OL. There will be 2 types of RD cohorts: 1) OL-RD and 2) randomized, DB, and placebo-controlled RD (referred to as DB-RD). Treatment-naïve subjects enter the SAD and DB-RD cohorts. Subjects in the SAD cohorts who complete the 90-day Follow-up Period can enter OL-RD cohorts. Details for each of these cohorts are described below.

Single Ascending Dose Cohorts

The SAD cohorts evaluate safety and PK of single doses of UX053 in treatment-naïve subjects. All subjects in the SAD cohorts will undergo a Screening Visit prior to their Baseline Visit. There are 3 planned SAD cohorts, each consisting of at least 2 subjects, all of whom will receive open-label UX053 ([Figure 1](#)). The planned dose escalation will proceed from 0.05 mg/kg in Cohort 1S, to 0.10 mg/kg in Cohort 2S, and to 0.20 mg/kg in Cohort 3S. An independent DMC will review at least 2 weeks of safety data for at least 2 subjects within a SAD cohort and the cumulative data from all subjects in prior dosing cohorts (when applicable) before deciding to proceed with the next SAD cohort.

Each subject in the SAD cohorts will be followed for a follow-up of 90 days after dosing. At the SAD Day 90 Visit, marking completion of the follow-up, subjects can be rescreened for entry into the OL-RD cohorts described below.

Open-Label Repeat Dosing Cohorts (Extension for SAD Cohorts)

The OL-RD cohorts serve as a short-term extension for subjects who participated in a SAD cohort. The OL-RD cohorts evaluate the safety and PK of 4 additional OL doses of UX053 in subjects who received a single dose of UX053 in a SAD cohort and completed the 90-day Follow-up Period. Subjects from the SAD cohorts are rescreened for participation in the OL-RD cohorts; eligibility for additional dosing in the OL-RD cohorts can be combined with assessments at the SAD Day 90 Visit.

During rescreening, a nutrition assessment will be completed at an Initial Screening Visit (ISV) to determine if the subject's diet meets the nutritional guidelines for adults with GSD III based on expert recommendations ([Table 2](#)). OL-RD subjects will proceed through rescreening as shown in [Figure 2](#) based on whether they meet these nutritional guidelines.

The first day of the ISV (which may coincide with the SAD Day 90 Visit) is followed by 3 consecutive days of nutrition diary collection. If a subject's diet during participation in a SAD cohort meets nutritional guidelines, and continues to do so at the ISV, the subject can proceed directly to the OL-RD Nutrition Stabilization Visit (STV) as soon as the ISV assessments are completed.

If the subject's diet does not meet nutritional guidelines, a Nutrition Optimization Visit (NOV) is performed. At this visit, nutritional counseling is provided to the subject on dietary changes needed to comply with GSD III-specific nutrition guidelines ([Table 2](#)). Nutrition diary and continuous glucose monitor (CGM) data will be reviewed by the Investigator and safety

laboratory tests may be obtained at the discretion of the Investigator. After 1 week of nutrition optimization (approximately 2 weeks after the ISV), the subject proceeds to the STV (occurring approximately 2 weeks before the subject's OL-RD Baseline/Week 0 Visit) and thereafter maintains a stable diet as defined by the nutritional guidelines for GSD III ([Table 2](#)) for the remainder of the study. If an OL-RD subject is unable to achieve an optimized diet, they are still eligible to proceed to the STV. The reason for the inability to achieve an optimized diet should be documented and the subject should make no substantial nutrition changes for the remainder of the study.

For selected sites and subjects, the OL-RD STV includes an optional controlled fasting challenge (CFC). Prior to the CFC, a morning cortisol is obtained between 6 and 9 am. The CFC is conducted during the subject's stay in the hospital, usually overnight, but can be conducted during the day. For the same sites and subjects, another optional CFC occurs at the Week 16 Visit; only subjects who completed the optional CFC at STV complete the CFC at Week 16. Additional details regarding the CFC are in Section [10.5.1](#).

Beginning with the OL-RD Baseline/Week 0 Visit, subjects in the OL-RD cohorts will receive 4 additional OL doses of UX053 Q4W at the same or lower dose than they received in the SAD cohorts, based on ongoing assessment of safety data.

Randomized, Double-Blind, and Placebo Controlled Cohorts

The DB-RD cohorts will evaluate the safety and PK of 5 doses of UX053 or placebo in treatment-naïve subjects. All DB-RD subjects will participate in a Screening Period (approximately 8 to 12 weeks) ([Figure 3](#)), in which subjects will be screened for study eligibility and assessed for the need to optimize their diet based on nutrition guidelines for adults with GSD III based on expert recommendations ([Table 2](#)). Within the first 2 weeks after the ISV, the Investigator will review nutrition diary data to determine if nutrition optimization is needed. If nutrition optimization is not needed, the STV occurs in clinic approximately 2 weeks after the ISV, and the Baseline/Week 0 Visit occurs approximately 4 weeks after the STV, to demonstrate 6 weeks of nutrition stability.

If nutrition changes are needed, a 2- to 4-week period of nutrition optimization will be performed to comply with GSD III-specific nutrition guidelines ([Table 2](#)). In this situation, the first NOV occurs as a phone visit approximately 2 weeks after the ISV. During nutrition optimization, NOV phone visits occur weekly or more frequently as needed; nutrition diary and CGM data are reviewed; and safety laboratory tests may be obtained at the discretion of the Investigator. Nutritional counseling is provided to the subject. When the Investigator determines that the subject has achieved nutritional optimization the STV is performed.

The Baseline/Week 0 Visit occurs as least 6 weeks after the STV. Due to the staggered nature of the cohorts (described below), a subject may be in nutrition stabilization for longer than 6 weeks before their Baseline Visit; in such instances, the total duration of the Screening Period may exceed 12 weeks. Nutrition guidance and monitoring for this study was established with available health authority guidance, and greater detail is available in the Study Reference Manual.

After the STV, no substantial nutrition changes should be made through the remainder of the study, notwithstanding temporary changes due to illness.

For selected sites and subjects, the DB-RD STV includes an optional controlled fasting challenge (CFC). Prior to the CFC, a morning cortisol is obtained between 6 and 9 am. The CFC is conducted during the subject's stay in the hospital, usually overnight, but can be conducted during the day. For the same sites and subjects, another optional CFC occurs at the Week 10 Visit; only subjects who completed the optional CFC at STV complete the CFC at Week 10. Additional details regarding the CFC are in Section [10.5.1](#).

In DB-RD cohorts, treatment-naive subjects will be randomized 3:1 to UX053 or placebo in ascending dose cohorts (4 subjects per cohort) ([Figure 1](#)). DB-RD subjects will receive study drug Q2W; a total of 5 doses of study drug are planned. The planned dose levels are 0.05 mg/kg in cohort DB-1R, 0.10 mg/kg in cohort DB-2R, and 0.20 mg/kg in cohort DB-3R.

Initiation of RD Cohorts (Both OL-RD and DB-RD)

Initiation of RD cohorts is as follows:

- Initiation of Cohort DB-1R and OL-1R will be guided by DMC review of at least 2 weeks of safety data from at least 2 Cohort 2S subjects and any available data from all subjects in prior and ongoing cohorts.
- Initiation of Cohort OL-2R and DB-2R will be guided by DMC review of either 1) at least 6 weeks of safety data from at least 4 subjects within Cohort DB-1R or 2) at least 12 weeks of safety data from at least 3 subjects within Cohort OL-1R (whichever is available first). In both of these scenarios, all available data from all subjects in prior and ongoing cohorts will also be reviewed.
- Initiation of Cohort OL-3R and Cohort DB-3R will be guided by DMC review of either 1) at least 6 weeks of safety data from at least 4 subjects within Cohort DB-2R or 2) at least 12 weeks of safety data from at least 3 subjects within Cohort OL-2R (whichever is available first). In both of these scenarios, all available data from all subjects in prior and ongoing cohorts will also be reviewed.

Cohort- and Subject-level Dose Selection and Modification for All Cohorts (SAD, OL-RD, and DB-RD)

At any time Ultragenyx may decide not to initiate a planned dose cohort. Dose levels for each cohort may be altered depending on safety, PK, and/or PD findings from prior cohorts. If needed to evaluate safety and dose-response relationships, additional cohorts may be added to test doses up to 0.30 mg/kg or additional subjects may be added to a cohort at the discretion of Ultragenyx to further characterize safety, PK, and PD effects, with input from the DMC. In every case, the safety of a single dose will be evaluated prior to repeat doses at the same dose level.

If a subject in an RD cohort develops a treatment-emergent adverse event (TEAE)/serious TEAE \geq Grade 3 that is considered by the Investigator to be related to study drug or an intolerable TEAE, subject-level dose reductions are allowed in consultation with the Medical Monitor. Ultragenyx will notify the DMC immediately if any subject experiences an event that satisfies subject-level stopping criteria (Section [8.3.2](#)) or study-level stopping criteria (Section [8.3.3](#)).

Glucose and Nutrition Data Collection by Study Subjects

At the Screening Visit for the SAD cohorts and ISV for the DB-RD cohorts, all subjects will receive CGM and handheld glucometer (HHG) devices and will be trained on the proper use of

these devices. Subjects will also be trained on completion of the nutrition diary During screening. Subjects entering the OL-RD cohorts do not need to be retrained if compliance was acceptable during participation in the SAD cohorts. When CGM data is being collected, all subjects will connect their CGM and HHG devices to a study-provided laptop weekly and upload CGM and HHG data. At remote visits, in conjunction with assessments performed by a home health nurse, the site will contact subjects by telephone or videoconference to confirm the CGM device is properly in use and data was uploaded; answer any questions regarding or help troubleshoot (if necessary) CGM device use; and review CGM data, HHG data (when applicable), and nutrition diary entries; outside of scheduled visits, these telephone calls will occur as needed. At in-clinic visits, a conversation between the site and the subject should occur to ensure CGM compliance and troubleshoot if needed.

Drug Administration, Dose Interval, and Blinding

UX053 will be administered as an intravenous (IV) infusion over the course of at least 4 hours, with a slower rate of infusion for the first hour to minimize the risk of hypersensitivity or anaphylactoid-type reactions (refer to the Pharmacy Manual for additional infusion details) ([Table 3](#) and [Section 9](#)). The infusion rate may be slowed to minimize the risk of IRRs in individual subjects.

Premedication and Rescue Medication

All subjects, including those treated with placebo, will receive premedication at least 1 hour prior to the infusion, consisting of oral paracetamol/acetaminophen (500 mg) or ibuprofen (400 to 800 mg), an H2 blocker (eg, famotidine 20 mg or equivalent dose of another H2 blocker), and an H1 blocker (eg, cetirizine 10 mg or equivalent dose of another H1 blocker). For the premedication, paracetamol/acetaminophen is preferred over ibuprofen.

At the discretion of the Investigator, with input from Ultragenyx and the DMC, and based on the emerging safety profile of UX053, additional premedications and rescue medications may be used to reduce the risk and severity of immune reactions in RD cohorts. Premedication and rescue medication selection will be based on the nature of the reactions being observed and the risks of such medications in patients with GSD III.

If a subject develops an IRR that meets diagnostic criteria for anaphylaxis ([Section 8.3.3](#)), epinephrine should be administered as initial rescue medication. For all other hypersensitivity reactions \geq Grade 2 in severity suspected to be due to immune activation, dexamethasone should be the initial rescue medication. The Medical Monitor must be notified if any rescue medication is used.

If dexamethasone (or equivalent) is used as a rescue medication, premedication with dexamethasone (or equivalent) should be considered for that subject's subsequent infusions after discussion with the Medical Monitor.

[Section 8.3.2](#) provides subject-level redosing criteria, stopping criteria, and additional instructions on how to proceed in the event of an IRR.

Subjects will have cardiorespiratory monitoring throughout the infusions and will stay overnight for visits in which they receive study drug and be observed in an inpatient or observational unit for 24 hours after the end of each infusion. Prior to discharge, all the following criteria must be met:

- All scheduled study assessments have been completed.
- No evidence of vital sign instability or clinical instability in the opinion of the investigator.
- Any signs or symptoms of potential IRRs are resolving or resolved.

Guidance on signs and symptoms that subjects should be vigilant for upon discharge and how to proceed in the event that these signs and symptoms manifest are provided in Section [9.1.4](#).

In each SAD cohort, subjects will be dosed sequentially with review of safety laboratory data from the 24-hour time point prior to dosing of the next subject. Within SAD cohorts, dosing of individual subjects will occur at a minimum interval of 72 hours. For example, the second subject in a cohort receives their first dose after a minimum of 72 hours after the first subject in the same cohort received their first dose. Subjects within a given RD cohort can be dosed simultaneously. After the first dose, DB-RD subjects maintain a Q2W dosing regimen and OL-RD subjects maintain a Q4W dosing regimen.

Subjects may receive COVID-19 vaccines during participation in the study. To facilitate discrimination of UX053 IRRs and adverse effects of vaccine administration, vaccines should not be administered within 48 hours after the most recent administration of UX053 and until safety labs obtained have been reviewed and the subject has been assessed for any possible hypersensitivity reaction to the most recent dose of UX053 (Section [9.1.6](#)).

For the DB-RD cohort, the subjects, Investigators, and site staff will be blinded to the treatment. Due to the difference in the opacity of UX053 and placebo, an unblinded pharmacist will prepare the investigational product (IP) and an unblinded nurse will prepare the infusion before masking the infusion syringe and tubing with colored covers.

The full schedules of events for the SAD, OL-RD and DB-RD, cohorts are listed in [Table 4](#), [Table 5](#), and [Table 6](#), respectively. Additional details regarding the timing of assessments before, during, and following treatment infusion are provided in [Table 7](#) for vital signs and [Table 8](#) for PK samples.

Although they are eligible, it is expected that few patients with GSD IIIb, IIIc, or IIId will enroll. Subjects with GSD IIIb/c/d will participate in all assessments, including muscle imaging and function tests, and will be included in all safety analyses. Sensitivity analyses for cardiac and skeletal muscle endpoints may exclude patients with GSD IIIb/c/d as described in the SAP.

Future protocol amendments may occur to include pediatric subjects with GSD III or the addition of an open-label extension for all subjects after an interim review of safety, PK, and PD data.

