DB, double-blind; DMC, Data Monitoring Committee; GSD, Glycogen Storage Disease; IV, intravenous; Q2W, every 2 weeks; Q4W, every 4 weeks; RD, Repeat Dose; SAD, Single Ascending Dose.

In each SAD cohort, subjects will be dosed sequentially with review of safety laboratory data from the 24-hour time point prior to dosing of the next subject. Within SAD cohorts, dosing of individual subjects will occur at a minimum interval of 72 hours. For example, the second subject in a cohort receives their first dose after a minimum of 72 hours after the first subject in the same cohort received their first dose. Subjects within a given RD cohort can be dosed simultaneously. After the first dose, DB-RD subjects maintain a Q2W dosing regimen and OL-RD subjects maintain a Q4W dosing regimen.

Subjects may receive COVID-19 vaccines during participation in the study. To facilitate discrimination of UX053 IRRs and adverse effects of vaccine administration, vaccines should not be administered within 48 hours after the most recent administration of UX053 and until safety labs obtained have been reviewed and the subject has been assessed for any possible hypersensitivity reaction to the most recent dose of UX053 (Section 9.1.6).

For the DB-RD cohort, the subjects, Investigators, and site staff will be blinded to the treatment. Due to the difference in the opacity of UX053 and placebo, an unblinded pharmacist will prepare the investigational product (IP) and an unblinded nurse will prepare the infusion before masking the infusion syringe and tubing with colored covers.

The full schedules of events for the SAD, OL-RD and DB-RD, cohorts are listed in [Table 4](#), [Table 5](#), and [Table 6](#), respectively. Additional details regarding the timing of assessments before, during, and following treatment infusion are provided in [Table 7](#) for vital signs and [Table 8](#) for PK samples.

Although they are eligible, it is expected that few patients with GSD IIIb, IIIc, or IIId will enroll. Subjects with GSD IIIb/c/d will participate in all assessments, including muscle imaging and function tests, and will be included in all safety analyses. Sensitivity analyses for cardiac and skeletal muscle endpoints may exclude patients with GSD IIIb/c/d as described in the SAP.

Future protocol amendments may occur to include pediatric subjects with GSD III or the addition of an open-label extension for all subjects after an interim review of safety, PK, and PD data.

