^a Screening assessments can be done over the course of multiple days. There must be a minimum of 10 days between any assessments that are measured at both the Screening and the BL Visit.

^b At the Day 90 Visit, marking completion of the Follow-up Period, subjects can be rescreened for entry into the OL-RD cohorts. Subjects must sign informed consent to enter into OL-RD cohorts prior to rescreening. Only EOS I Day 90 Visit assessments are included in the table above; please refer to [Table 5](#) for assessments that should be performed for rescreening for OL-RD. If rescreening for OL-RD occurs in conjunction with the SAD EOS I Day 90 visit, assessments in common should not be duplicated.

^c In the event a subject has an ET, all efforts will be made to monitor the subject through the end of the study. At minimum, a safety follow-up phone call will occur within the 4 weeks following the subject's last treatment.

^d Complete physical exam is required at the Screening, BL, and EOS I/ET Visits. Targeted physical exams may be performed at the D1 Visit.

^e Assessments to be performed prior to dosing. The following assessments can be collected within a week prior to dosing, as long as there is a minimum of 10 days between assessments that are repeated at the Screening Visit and the Baseline Visit: HHD, PROMIS questionnaires, SF-36v2, and GNEM-FAS expanded version.

^f Refer to [Table 7](#) for the timing of vital sign assessments during dosing.

^g Refer to [Table 8](#) for details of PK sampling. Please note that sample collections are marked for D1, D4, D7, D14, D21, and D28 in this table ([Table 4](#)) corresponding to a sample collection 1, 4, 7, 14, 21, and 28 days after infusion of UX053 on D0 as outlined in the final rows of the first column in [Table 8](#).

^h Sample to be collected pre-dose and at the end of the infusion. Post-infusion blood samples should be collected in the opposite arm of the infusion to avoid dilution.

ⁱ Close monitoring is required for subjects who develop elevations in ALT > 3x ULN and > 2x their baseline value, or elevation in ALT > 3x ULN with INR > 1.5. This includes repeating liver enzymes and INR within 48 hours and consideration of additional diagnostic tests such as liver ultrasound ([Section 10.1.5](#)).

^j All efforts should be made for urine collections to be consistently taken from the first morning void.

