8.2. Exclusion Criteria

Each subject must not meet the exclusion criteria listed below at screening (ISV for DB-RD cohorts) and baseline (Day 0 for SAD cohorts or Week 0 in all RD cohorts), as applicable, to be enrolled in the study:

1. History of liver transplant, including hepatocyte cell therapy/transplant, or active listing for liver transplant
2. History of cirrhosis, or presence of any of the following:
 - a. Total bilirubin \geq 1.3 mg/dL and INR \geq 1.3
 - b. Evidence of portal hypertension, including, but not limited to the following symptoms splenomegaly, ascites, thrombocytopenia, esophageal varices, or history of hepatic encephalopathy
 - c. Model for End Stage Liver Disease (MELD) score $>$ 12
3. Current Hepatitis B or C infection or history of chronic Hepatitis B or C infection
4. Severe renal impairment defined as a glomerular filtration rate (GFR) \leq 29 mL/min ([Levey et al., 2005](#)).
5. Any prior history of hepatocellular carcinoma or presence of liver adenoma $>$ 5 cm at the longest diameter or $>$ 3 cm and \leq 5 cm in size that has an annual growth rate of \geq 0.5 cm per year
6. Current or history of malignancies in the 3 years prior to the Screening Visit (ISV for RD)
7. Hospitalizations related to GSD III disease between the Screening (ISV for RD) and Baseline Visit
8. Known history of human immunodeficiency virus infection
9. Presence or history of any hypersensitivity reactions requiring medical evaluation and management (including injection/IRRs, such as lymphadenopathy) to UX053, its excipients, or any drug products that contain polysorbate or PEG. This may include vaccines that contain PEG or polysorbate
10. Significant cardiac disease, including heart failure with New York Heart Association (NYHA) Function Capacity III or IV or Objective Assessment C or D, unstable angina, or ejection fraction (EF) $<$ 35%, or uncontrolled arrhythmia or resistant hypertension ([Carey et al., 2018](#)). Mild cardiomyopathy and left ventricular hypertrophy (LVH) are allowed
11. Presence or history of any co-morbid condition or abnormal labs that, in the view of the Investigator, places the subject's safety at risk; places the subject at high risk of poor

treatment compliance or not completing the study; or would significantly affect the interpretation of study results

12. Poorly controlled diabetes, defined as the presence of any of the following:
 - a. Hemoglobin A1C > 8% ([Qaseem et al., 2018](#))

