 - b. History of diabetic nephropathy, neuropathy, or retinopathy
 - c. History of diabetic ketoacidosis during the past year
13. Poorly controlled hypothyroidism, based on the judgement of the Investigator or Ultragenyx, whichever is most conservative
14. History of chronic coagulopathy, thrombophilia, or disorder of complement activation
15. Use of concomitant medications that alter prothrombin time/international normalized ratio (PT/INR), including warfarin and direct oral anticoagulants (eg, rivaroxaban, apixaban, and edoxaban). Patients who receive medications that affect platelet function, such as aspirin or clopidogrel, are allowed unless they have comorbidities that in the judgment of the Investigator place them at undue risk to participate in the study.
16. Current treatment with long-term immunosuppressive medications. This includes subjects with autoimmune conditions managed with immunosuppressive medications and solid organ transplant recipients.
17. Active tuberculosis requiring treatment in the past 3 years
18. Symptomatic COVID-19 infection
19. History of active alcohol and/or drug abuse that in the Investigator's assessment would impair the subject's ability to comply with the protocol
20. Receipt of only 1 of 2 planned doses of a COVID-19 vaccine. Subjects who have not received a COVID-19 vaccine, and those who have completed COVID-19 vaccination are eligible.
21. Planned surgery, including dental surgeries, during the study
22. Pregnant or breastfeeding or planning to become pregnant (self or partner) at any time during the study
23. Females of childbearing potential with hepatocellular adenoma who are unwilling to use nonhormonal contraception
24. Use of any IP or investigational medical device within 30 days or for IP within 5 half-lives, whichever is longer, prior to screening (or rescreening, as applicable), or requirement for any investigational agent prior to completion of all scheduled study assessments
25. For subjects rescreening into OL-RD cohorts, any of the following after treatment with UX053 in a SAD cohort:
 - a. New or worsening symptoms of liver disease (including new or worsening hepatomegaly) along with any increase in transaminase levels
 - b. Receipt of any blood product administration (eg, packed red blood cells, platelet, FFP) for management of consumptive coagulopathy

- c. An ALT level that is $\geq 8x$ ULN and $> 2x$ the subject's baseline value in the absence of an alternative explanation

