9.1.6. Coronavirus Disease 2019 (COVID-19) Vaccination

Both UX053 and the mRNA-LNP vaccines for SARS-CoV-2 contain some of the same excipients, which are the LNP structural lipid components, namely CCI [REDACTED]

[REDACTED] Currently available mRNA-LNP COVID-19 vaccines also contain either the same CCI [REDACTED] or a similar CCI [REDACTED] as UX053. Patients who have experienced a severe hypersensitivity reaction in response to an mRNA-LNP vaccine are excluded from this study due to potential cross-reactivity of antibodies to UX053, such as CCI [REDACTED] antibodies (Section 8.2).

While COVID-19 vaccination is allowed during study participation, COVID-19 vaccines should not be administered within 48 hours after the most recent administration of UX053 and until safety labs obtained have been reviewed and the subject has been assessed for any possible hypersensitivity reaction to the most recent dose of UX053. The timing of COVID-19 vaccination doses will be captured in the case report form (CRF), as these would inform the interpretation of AEs.

If a subject has an immediate or severe hypersensitivity reaction to UX053, consultation with an allergist/immunologist is recommended prior to administration of an COVID-19 vaccine due to potential antibody cross-reactivity CCI [REDACTED] (Banerji et al., 2020). It is not known whether treatment with UX053 increases the likelihood of developing a severe hypersensitivity reaction to an mRNA-LNP vaccine. For additional information on potential interventions in the event of toxicity, please refer to the IB.

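### The COVID-19 vaccine rule sets a gap from infusion to vaccine but none from vaccine to infusion, so a vaccine reaction can be counted as an infusion-related reaction (minor)

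*Protocol*

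**What the plan says.** **Vaccine timing.** The synopsis and section 7.1 of the protocol carry the same rule. It opens with its aim and the 48-hour limit, counted from the UX053 dose: "To facilitate discrimination of UX053 IRRs and adverse effects of vaccine administration, vaccines should not be administered within 48 hours after the most recent administration". It then adds a wait for laboratory review: "vaccines should not be administered within 48 hours after the most recent administration of UX053 and until safety labs obtained have been reviewed". Section 9.1.6 repeats the limit: "COVID-19 vaccines should not be administered within 48 hours after the most recent administration of UX053". All three places also require that the subject be assessed for hypersensitivity to the latest UX053 dose before a vaccine is given. Section 9.1.6 has vaccine dates recorded on the CRF to help interpret adverse events.

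**Eligibility.** Under section 8.2 a patient "must not meet the exclusion criteria listed below at screening (ISV for DB-RD cohorts) and baseline (Day 0 for SAD cohorts or Week 0" for the repeat-dose cohorts). Criterion 20 excludes "Receipt of only 1 of 2 planned doses of a COVID-19 vaccine". It adds that unvaccinated patients may enter and that "those who have completed COVID-19 vaccination are eligible". It gives no minimum time since the last dose.

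**Redosing.** The criteria in section 8.3.2 concern liver tests, platelets, INR, blood products and infusion reactions. Vaccination is not mentioned.

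**Analysis.** Section 11.4 plans a summary of IRR incidence and severity by treatment and cohort. It defines an IRR by timing alone: any adverse event from the start of the infusion to 4 hours after its end, whatever the Investigator thinks of its cause.

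**The concern.** IRRs cluster around an infusion. The order of events most likely to blur an IRR with a vaccine reaction is therefore vaccine first and infusion soon after. The rule leaves that order open: a vaccine given the day before dosing complies with the protocol and defeats the rule's stated purpose.

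The protocol's own background shows that the symptoms overlap. In section 5.4.1.2, fatigue, chills and headache are three of the five adverse events reported by more than half of the 45 recipients of mRNA-1273. All three are also among the IRR symptoms listed for patisiran.

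At stake is the IRR count by cohort. If the clinician also judges the event to be an IRR, so is its handling under Table 10: interruption and dexamethasone at Grade 2, no redosing at Grade 3 or above. Table 10 does not adopt the section 11.4 timing definition, so that second consequence depends on clinical judgement.

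**Working it through.** The plan gives no figure to reproduce. The check sets the rules side by side and then does interval arithmetic.

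**1. Is the open direction closed anywhere?**
- Synopsis, 7.1 and 9.1.6: infusion to vaccine only.
- Exclusion 9: history of hypersensitivity, not timing.
- Exclusion 20: a half-completed two-dose series, checked at screening and baseline and not before later infusions.
- Section 8.3.2: silent.

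What remains open is (a) a booster or single-dose vaccine shortly before a first infusion; (b) a two-dose series finished during the 8 to 12 weeks of DB-RD screening; (c) any vaccine dose before a later repeat infusion. A full series begun and finished within the roughly 2-week SAD screening is unlikely. That assumes the two doses are spaced further apart than this, which the documents do not state.

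**2. Length of the IRR window.** Infusion of at least 4 h plus 4 h afterwards: 4 + 4 = at least 8 h.

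**3. Days on which a vaccine is allowed now.** Dosing interval minus the 2-day gap.
- Q2W: 14 − 2 = 12 days.
- Q4W: 28 − 2 = 26 days.

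**4. Share of those days that fall in the last 48 h before the next infusion.** Assumption: one vaccine, timed uniformly over the allowed days.
- Q2W: 2/12 = 16.7%.
- Q4W: 2/26 = 7.7%.
- If the laboratory review means the Day 7 tests described in section 5.5: 2/(14 − 7) = 28.6% and 2/(28 − 7) = 9.5%.

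These are chances of vaccine timing, not of a reaction starting inside the IRR window.

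**5. Where this applies.** As planned, DB-RD has 12 × 4 = 48 later infusions and OL-RD up to 6 × 3 = 18, together 66. SAP section 8 reports that the study ended with 4 subjects in Cohort 1S and 4 in Cohort 2S, and that only analyses of those cohorts will be provided. That is 8 × 1 = 8 infusions, all at Day 0, so steps 3 and 4 describe the design and not the reported data.

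**6. What one misclassified subject does.** In a SAD cohort as ended, 1/4 = 25 percentage points on that cohort's IRR incidence. This shows scale only. The documents give neither a vaccination rate nor reaction onset times, so no expected number can be calculated.

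**7. Days left if a vaccine-to-infusion gap is added.** The length is an assumption, so a range is shown.

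| Gap before infusion | Q2W, of 14 days | Q4W, of 28 days |
|---|---|---|
| 24 h | 11 | 25 |
| 48 h | 10 | 24 |
| 72 h | 9 | 23 |
| 7 days | 5 | 19 |

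With a 48 h gap and a wait for Day 7 tests, 14 − 9 = 5 and 28 − 9 = 19 days remain.

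**The case against.** The case against has real weight.

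- **The confounder is recorded.** Vaccine dates are on the CRF, and vaccines are also captured as concomitant medications (section 10.1.8).
- **Reactions already under way should be noticed.** Vital signs, examination and blood samples precede each infusion. Under Appendix 1 a pre-existing condition is a new adverse event only if it worsens.
- **Cause is judged separately.** Appendix 1 asks the Investigator to weigh other therapies, and section 11.4 reports events by relationship to study drug.
- **Section 11.4 is broad by design.** Intercurrent illness or premedication effects enter the IRR count too.
- **The rule has a second purpose.** Section 9.1.6 also protects subjects who react to UX053 from a vaccine with shared excipients, and that purpose runs in one direction.
- **The output may not exist.** The SAP takes precedence on analysis. Its visible safety sections contain no IRR table, although the redacted tertiary sections could hold one.
- **The 48 hours has no onset data behind it.**

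All of this limits the size, and most of it stands. None of it supplies the missing interval, and neither document has a rule that uses the recorded dates to flag an event.

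A reader might go further in three ways that the documents do not support:
- **That 66 of 90 planned infusions (73%) were at risk.** These are infusions without a limit, not vaccine exposures, and they lie outside the analyses to be provided.
- **That the one-way rule makes matters worse.** With no rule the shares in step 4 would be 2/14 = 14.3% and 2/28 = 7.1%. The rise to 16.7% and 7.7% comes only from assuming that displaced vaccines spread evenly. If they simply move to the third day, nothing changes.
- **That the primary safety result is biased.** After a subject's first UX053 dose, a vaccine reaction is treatment-emergent whenever the vaccine was given. The gap can alter TEAE status, or the section 8.3.3 pause, only around that first dose. OL-RD Week 0 is not such a dose, because those subjects were already treated in a SAD cohort.

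**Conclusion.** The point holds as a minor design gap. The rule states the aim of discriminating IRRs from vaccine effects but controls only one order of events, and the order left open is the more confusing one. Section 11.4 then counts a vaccine reaction as an IRR if it starts or worsens in the window.

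The size is small. The IRR summary is not the primary endpoint, no primary or secondary conclusion is shown to change, and no count of misclassified events can be given. For the study as ended, the exposure is a booster or single-dose vaccine shortly before Day 0 in 8 subjects. The conclusion rests on the current text containing no other timing rule. The step 4 percentages rest further on uniform vaccine timing, and the conclusion does not need them.

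**What to change.** Add one sentence to the synopsis, 7.1 and 9.1.6, and apply it at baseline beside exclusion 20: *Study drug should not be infused within 48 hours after any COVID-19 vaccine dose, nor until any reaction to that dose has been assessed.* The 48 hours mirrors the existing gap; the safety lead should confirm or lengthen it. In the adverse event listings, add time since the last vaccine dose from the CRF dates, and flag any TEAE or IRR with onset inside the interval.

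The cost is one clause in three places, one line at baseline and one listing column. An occasional infusion or vaccine moves by about two days. For a repeat dose that fits the ±2 day window in Tables 5 and 6, though a longer wait for a reaction to be assessed may not. For SAD Day 0, Table 4 sets only a lower limit on the spacing from screening ("There must be a minimum of 10 days between any assessments that are measured at both the Screening and the BL Visit"), so a short delay is possible.

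For the ended study only the listing flag can still be applied. The clause belongs in any future repeat-dose protocol for UX053.
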